### **PROCEDURES**

# **Research Design**

Patients from the high-risk sample (primary target population) will be randomly assigned to one of 4 study arms. Outcomes during the 2020-2021 flu season will be compared between study arms

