### Exclusion Criteria:

• Same as primary target population

> **Recruitment and Enrollment.** All patients meeting the primary target population criteria will be enrolled into one of the 4 experimental conditions. Anticipated enrollment number for this primary target population is 56,000. Only patients from this primary target population will be contacted. However, health record data will be accessed to assess secondary outcomes for household members of this target population (expected N of 234,000) and for patients whose risk scores were calculated by Medial's ML algorithm and determined to fall just below the high-risk cutoff (expected N of 56,000). This brings the total planned enrollment to 346,000 participants.

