Because this intervention is timed to the 2020–21 flu season, the intervention period will begin ~9/1/20 and last for three months. During that period, all identified primary target population participants will be randomized and will receive 1–3 separate messages (content based on their assigned condition) in sequence via postal letter, SMS, and patient portal modalities, using all modalities available for each participant. Outcomes will be measured as of 5/31/21. Data extraction from the EHR, data cleaning, data analysis, and manuscript preparation will begin on or after 6/1/21 and will include data from not only the primary target population but also the two secondary populations.

> The primary study outcomes will be the rates of flu vaccination and flu diagnoses during the 2020–21 season (start of intervention through 5/31/21) by the primary target population. We will also measure secondary, exploratory outcomes: Rates of flu vaccination and diagnoses by fellow household members of targeted patients; rates of flu vaccination and diagnoses by non-targeted patients who were assigned a risk score that fell just below the cutoff of targeted patients; rates of flu complications and flu-like symptoms among targeted patients, household members, and those at sub-threshold risk; and rates of other relevant healthcare utilization outcomes such as ER visits and hospitalizations.

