Encouraging Flu Vaccination Among High-Risk Patients Identified by a Machine-Learning Model of Flu Complication Risk

NCT04323137

January 8, 2021

Statistical Analysis Plan

Project Status

All intervention messages have been disseminated. Data collection is ongoing, but an interim data analysis step will be conducted to inform COVID-19 vaccination efforts.

Planned Analyses

Primary Analyses:

Question 1: Does informing patients that they are at high risk for flu complications (a) increase the likelihood that they will receive flu vaccine; and (b) decrease the likelihood that they receive diagnoses of flu and/or flu-like symptoms in the ensuing flu season?

Analysis 1: We will evaluate if patients who are informed about their risk status (patients who were randomized to "high risk" message groups 2, 3, or 4 in the Study Design) exhibit improved flu vaccination and diagnosis rates compared with patients who were not informed (randomized to the control condition, group 1). To assess this, we will employ a generalized linear model with a binary distribution and log-link function (i.e. a logistic regression).

Question 2: Does informing patients that their high-risk status was determined (a) by analyzing their medical records (group 3) vs. by no specified method (group 2); and (b) by an AI/ML algorithm analyzing their medical records (group 4) as opposed to via unspecified methods or human medical records analysis affect the likelihood that they receive the flu vaccine and/or diagnoses of flu and/or flu-like symptoms in the ensuing flu season?

Analysis 2: We will evaluate this using 3 logistic regression models, comparing patients in groups 2 and 3, 2 and 4, and 3 and 4. Reported p-values will be adjusted for family-wise error rate across the three comparisons using Holm's procedure.

For both analyses described above, we will first assess the intraclass correlation (ICC) for patient-visited PCPs and/or clinics; if the ICC is greater than 0.1, a mixed model will be used with this variable included as a random effect.

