Patients who received an intervention message (groups 2, 3, and 4) may have received communications via up to 3 modalities. We will employ logistic regression to evaluate the impact of modality on outcomes of interest, assessing pairwise comparisons of the following modality combinations: letter only, letter + myGeisinger, letter + SMS, or letter + myGeisinger + SMS. The small number of patients who did not experience one of these modality combinations will be excluded for this analysis.

Impact of risk level and framing

We will evaluate the impact of risk level (top 3rd percentile vs. remaining 3-10th percentile) as a moderator for Analysis 1 and risk framing ("top 3%", "top 10%", "high") as a moderator for Analysis 2, assessing if the moderators interact with experimental group to affect study outcomes. As described in Analysis 3, risk framing will be dummy coded with "top 10%" as the reference level.

Analysis Exclusion Criteria

A small number of deceased patients and patients who received the flu vaccination before the start of the intervention were unintentionally included in this study. These patients will be

excluded from all analyses. Another small population of patients' print letters were returned to sender; these patients will remain included in analyses but will be documented as having not been contacted through this modality. Finally, due to delays in intervention rollout, there were patients who were vaccinated prior to the start of the study (9/21/20). These patients will be excluded from all above analyses, as they were not intended to receive the intervention.

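### Holm in Analysis 2 is valid but stricter than three linked pairwise comparisons need; Shaffer's procedure is an optional improvement at the same family-wise level

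*SAP*

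**What the plan says.** SAP, Primary Analyses, Analysis 2: "We will evaluate this using 3 logistic regression models, comparing patients in groups 2 and 3, 2 and 4, and 3 and 4". The next sentence sets the multiplicity rule: "Reported p-values will be adjusted for family-wise error rate across the three comparisons using Holm's procedure". The family is therefore every pairwise comparison among the three message groups.

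Question 2 asks whether the stated source of the risk finding would "affect the likelihood that they receive the flu vaccine and/or diagnoses of flu and/or flu-like symptoms in the ensuing flu season", so the tests read as two-sided and are repeated for each outcome. Under Secondary Analyses, the SAP carries the same approach over to the secondary outcomes.

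Neither document gives a family-wise level, an effect size or a power figure for Question 2. Neither mentions a closed or gatekept procedure, or a global test of groups 2 to 4.

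**The concern.** Holm makes no assumption about how the hypotheses relate to each other. Its second step, at alpha/2, guards against the case where two nulls are still true after one has been rejected. With all pairs of three groups that case cannot arise, so the step spends power on protection that is not needed.

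What is at stake is the second contrast to be declared. Question 2(b) sets the algorithm message against both the unspecified message (group 2) and the medical-records message (group 3). A full positive answer needs both 2 vs 4 and 3 vs 4, and Holm's second step makes that joint conclusion harder to reach.

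**Working it through.** **Inputs from the documents**
- Family: 2 vs 3, 2 vs 4 and 3 vs 4, adjusted by Holm (SAP, Analysis 2).
- Size: "Anticipated enrollment number for this primary target population is 56,000" (Protocol, Recruitment and Enrollment).
- Arms: "Patients from the high-risk sample (primary target population) will be randomly assigned to one of 4 study arms" (Protocol, Research Design).
- Outcomes: "The primary study outcomes will be the rates of flu vaccination and flu diagnoses during the 2020–21 season" (Protocol, Detailed Study Procedures); these are binary.

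**Assumptions, because the documents are silent**
- Equal allocation: 56,000 / 4 = 14,000 per arm.
- No loss from the SAP's post-randomisation exclusions, whose number is not given.
- Two-sided tests and a 5% family-wise level. The logic holds at any alpha.
- A 50% base rate, with a range of differences; also 2% vs 2.5% for a rarer outcome.

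The plan has no power figure to reproduce.

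**Step 1: which sets of nulls can be true.** If groups 2 and 3 are equal and groups 2 and 4 are equal, then groups 3 and 4 are equal. The number of true nulls is 3, 1 or 0. Once one null is false, at most one of the other two can be true.

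**Step 2: thresholds for the ordered p-values at 5%**
- Holm: 0.05/3 = 0.01667, then 0.05/2 = 0.025, then 0.05.
- Shaffer: 0.05/3 = 0.01667, then 0.05, then 0.05.

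The decisions differ only when p(1) is at most 0.01667 and p(2) lies above 0.025 and at or below 0.05. The third threshold is the same under both, although Shaffer reaches it more often. Shaffer rejects everything that Holm rejects.

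**Step 3: what the threshold means for one pair.** The standard error of a difference near 50% is sqrt(2 × 0.25 / 14,000) = 0.598 points. The difference detectable with 80% power is:
- at 0.025: (2.241 + 0.842) × 0.598 = 1.84 points;
- at 0.05: (1.960 + 0.842) × 0.598 = 1.67 points (before rounding of the standard error).

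**Step 4: simulation.** 400,000 replicates of three arms of 14,000, with pooled two-proportion z-tests standing in for the logistic models. With groups 2 and 3 at 50% and only group 4 higher, the chance of declaring both algorithm contrasts changes as follows.

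| Difference (points) | Holm | Shaffer | Gain (points) |
|---|---|---|---|
| 0.5 | 2.3% | 3.8% | 1.5 |
| 1.0 | | | 5.8 |
| 1.5 | 44.5% | 53.8% | 9.3 |
| 2.0 | 78.2% | 84.7% | 6.5 |
| 2.5 | | | 1.9 |
| 3.0 | | | 0.2 |
| 4.0 | | | 0 |

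Blank cells: only the gain was tabulated.

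Other patterns:
- Per true contrast: 57.8% to 62.5% at 1.5 points, and 85.7% to 88.9% at 2 points.
- Graded 50/51/52%: each adjacent contrast goes from about 30% to about 38%. Graded 50/50.5/51%: 7.1% to 9.5%. Graded 50/52/54%: 91.7% to 91.9%.
- Rarer outcome, 2/2/2.5%: both contrasts, 58.1% to 67.0%.

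**Step 5: what does not change.** The first step is alpha/3 under both rules, so the chance of at least one rejection is identical: 71.2% at 1.5 points and 93.1% at 2 points.

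**Step 6: error rate.** With all three groups equal, the family-wise error is 4.4% under both rules. When only group 4 differs, the chance of falsely rejecting 2 vs 3 goes from Holm to Shaffer as follows:
- 1 point: 2.3% to 4.0%;
- 1.5 points: 2.9% to 4.8%;
- 2 points: 3.9% to 5.0%.

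**The case against.** The strongest reply is that nothing here is wrong. Holm is prespecified and controls the family-wise error, and the choice among valid procedures is partly preference. That stands, and it is why this is graded as optional.

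Four further points also stand.
- The gain is concentrated at differences of roughly 1 to 2.5 points. It is negligible for very small differences and for differences of 3 points or more.
- A reader might infer that the change costs nothing in any scenario. It costs no power, but the actual false-positive rate rises within the 5% limit. The rule covers only the three comparisons within an outcome, and Analysis 2 is applied to more than one outcome. Multiplicity across outcomes is a separate matter that Shaffer does not address.
- A reader might infer that the contrasts are expected to be small, so that the gain is assured. The Protocol's background section gives a hypothesised direction, a positive reaction to the algorithm, but no size.
- If power were the only aim, a closed test opening with a 2-df global test of groups 2 to 4 does slightly better. At 1.5 points it gives 56.3% for both contrasts, against 53.8% with Shaffer, and it raises the chance of any finding from 71.2% to 74.1%. It is a larger change, since it adds a test that the SAP does not contain.

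Timing is a real constraint. By the SAP's date, January 8, 2021, all messages had been sent and an interim analysis was planned. Moving to a more liberal rule after arm-level results are known would not be credible as a primary analysis.

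**Conclusion.** The point holds as an efficiency gain. Holm's second step is stricter than family-wise control requires for this family, and Shaffer's procedure dominates it in power at the same nominal level. Under the stated assumptions (14,000 per arm, 50% base rate, 5% level, only group 4 differing), the gain in declaring both algorithm contrasts is about 6 points at a 1-point difference, 9 at 1.5, 6.5 at 2, and about 0 from 3 upwards. The logic does not depend on these assumptions; the size of the gain does.

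Two stronger readings should be resisted. The plan does not contain a multiplicity error: Holm does what the SAP says it does. Nor does Holm make it less likely than Shaffer that Question 2 yields any finding at all. What improves is the ability to declare a second or third contrast after a first success.

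**What to change.** In Analysis 2, replace Holm with Shaffer's procedure for the three pairwise comparisons, applied separately to each outcome. With p(1) ≤ p(2) ≤ p(3):
- adjusted p(1) = 3 × p(1);
- adjusted p(2) = max(adjusted p(1), p(2));
- adjusted p(3) = max(adjusted p(2), p(3));
- each capped at 1.

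State the family-wise level and that the tests are two-sided, since the SAP gives neither.

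The three separate models can stay in the base case. With group as the only predictor, one model with a three-level group factor gives the same log odds ratios and standard errors. The single model matters only if the ICC exceeds 0.1 and the mixed model is used; the three contrasts should then come from one fit.

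Record, with a date, that the change was made before anyone saw arm-level results, including those of the interim analysis. If that cannot be shown, keep Holm as primary and report Shaffer as a sensitivity analysis.

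The cost is one SAP sentence plus that record, with no extra data. In return, the plan accepts an actual false-positive rate nearer to the 5% limit.

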## **Detailed Study Procedures.**

Eligible patients will be randomly assigned to one of 4 experimental conditions:

- 1. **Control**: In this condition, patients will receive no additional pro-vaccination intervention beyond Geisinger's normal efforts. Note that these efforts include a variety of Marketing and other system campaigns designed to encourage all patients and members to get their flu shot. In addition, the care gaps team has an annual campaign to encourage flu shots that targets patients who are determined by a non-ML assessment that they are at high risk for complications and we expect there to be overlap between this group of patients and the ML high-risk group we will be contacting. (Because the care gap team's high-risk patients are not told that they are at high risk or that they have been targeted, we are not concerned that this ongoing campaign will interfere with our ability to measure the effects of high-risk communication.)
- 2. **High Risk Only**: In this condition, patients will receive messages telling them they are at high risk for flu complications without specifying how/why Geisinger believes this to be the case.
- 3. **High Risk Based on Medical Records**: In this condition, patients will receive messages telling them they have been identified to be at high risk for flu complications via analysis or review of their medical records. This is an accurate statement, since it does not specify that a human conducted this review or analysis. However, we anticipate that most readers will assume it was a human rather than an algorithm, allowing us to compare attitudes towards human versus machine risk determination.
- 4. **High Risk Based on Algorithm**: In this condition, patients will receive messages telling them they have been identified to be at high risk for flu complications via analysis of their medical records by AI/ML.

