Question 3: Patients in each of the conditions were stratified based on whether they were in the top 3rd percentile of risk, or in the subsequent 3rd-10th percentile. Patients in the former group were always told they were in the "top 3%" of risk. Patients in the latter group were either told they were in the "top 10%" of risk or that they were at "high" risk. These different risk conditions will be used to ask whether a) patients with the same risk level are affected by a vague verbal ("high") vs. specific numeric ("top x%") risk framing and b) patients with the same numeric risk phrasing are differentially affected due to different specific risk levels (3% vs. 10%). Analysis 3: We will evaluate this using a single logistic regression model with "top 10%" condition dummy coded as the reference level. This will allow the contrasts of "top 10%" vs. "high" (for question 3a) and of "top 10%" vs. "top 3%" (for question 3b).

Secondary Analyses:

We will use the approaches in Analyses 1 and 2 to evaluate the impact of the intervention on the secondary outcome measures listed in the pre-registration.

Exploratory Analyses

Impact on timing of shot

This analysis will focus on the subgroup of patients who were vaccinated. We will employ linear regression models to compare the time it took to receive a flu shot for patients who were informed about their risk status with those in the control group (as in Analysis 1) and among the 3 risk status communication conditions (as in Analysis 2). Time will be specified as the number of days since the beginning of the intervention (September 21, 2020). If the distribution of the time variable is skewed so as to violate the assumptions of a linear regression, data will be log transformed or analyzed using a gamma model.

Impact of age

While older patients tend to be aware of their increased vulnerability, younger patients may be more surprised to learn of their high-risk status. We will therefore examine the differential response of patients above vs. below age 65 by introducing this age variable as moderator and assessing if it interacts with experimental group to affect vaccination behavior. We will also conduct this analysis using age as a continuous variable.

Impact of modality

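### The ICC rule covers only the individually randomised Analyses 1 and 2; the non-randomised contrast 3b and the modality comparisons have no clustering provision, so their standard errors can be too small

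*SAP*

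**What the plan says.** The clustering rule stands in the SAP under Primary Analyses, after Analysis 2 and before Question 3. It begins: "For both analyses described above, we will first assess the intraclass correlation (ICC) for patient-visited PCPs and/or clinics". It continues: "if the ICC is greater than 0.1, a mixed model will be used with this variable included as a random effect". Only Analyses 1 and 2 have been described by that point. The secondary outcomes probably inherit the rule by reference: "We will use the approaches in Analyses 1 and 2 to evaluate the impact of the intervention on the secondary outcome measures".

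Two later sets of models carry no such provision.

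- **Analysis 3**, also listed as primary: "We will evaluate this using a single logistic regression model with 'top 10%' condition dummy coded as the reference level".
- **Impact of modality**, listed as exploratory: "We will employ logistic regression to evaluate the impact of modality on outcomes of interest".

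On allocation, the protocol (Detailed Study Procedures) says: "Eligible patients will be randomly assigned to one of 4 experimental conditions". The exposure in contrast 3b follows the risk stratum, because under Question 3 every patient in the top three percentiles received the top-3% wording. Modality follows whatever channels each patient had available (protocol, Detailed Study Procedures). Neither exposure is randomised. For contrast 3a (top-10% against vague high-risk wording within one stratum), the SAP does not say how the wording was assigned.

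**The concern.** When clustering is ignored, a patient-level contrast gets the wrong standard error only if the outcome and the exposure both cluster. Individual randomisation removes the second condition. The plan therefore checks clustering where it cannot inflate type I error, and omits the check where it might. At stake is whether a primary contrast (3b) and the modality results are reported with intervals that are too narrow.

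The rule is also loose within Analyses 1 and 2. It reads the outcome data before choosing the model, names no ICC scale, and leaves the cluster unit open between PCP and clinic. In logistic regression, adding a random effect also moves the target from a marginal to a cluster-conditional odds ratio. The data could therefore choose which kind of odds ratio is reported.

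**Working it through.** **Inputs from the documents.** ICC threshold 0.1 (SAP); four arms with patient-level assignment and 56,000 patients expected (protocol). The documents give no ICC, cluster size or power calculation behind the threshold, so there is no plan figure to reproduce.

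**Assumptions, not in the documents.** Equal arms (14,000 each); 50% vaccination rate; a 1-point effect for the power illustration; 25 to 100 patients per cluster within the contrast; outcome ICC 0.05 to 0.09 (below the gate); exposure ICC 0 to 0.10.

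**1. Randomised contrasts (Analysis 1, 14,000 against 42,000).** Ignoring clustering inflates the variance, relative to modelling it, by about 1/(1 − ICC):

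- ICC 0.02: 1/0.98 = 1.02
- ICC 0.05: 1/0.95 = 1.05
- ICC 0.10: 1/0.90 = 1.11

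SE of the risk difference = √[0.25 × (1/14,000 + 1/42,000)] = 0.00488. Power for a 1-point difference is Φ(0.01/0.00488 − 1.96) = 53.6%. With an ICC of 0.10 modelled, the SE is 0.00488 × √0.90 = 0.00463 and power is 57.9%. A simulation that ignored clusters of 100 gave type I error of 5.2% at ICC 0.05 and 5.0% at ICC 0.10. The error rate holds; only some precision is lost.

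**2. Non-randomised contrasts.** Variance inflation D = 1 + (m − 1) × ICC of outcome × ICC of exposure. The true SE is √D times the reported SE. Type I error = 2 × [1 − Φ(1.96/√D)].

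| m | Outcome ICC | Exposure ICC | D | √D | Type I error |
|---|---|---|---|---|---|
| any | any | 0 | 1.00 | 1.00 | 5.0% |
| 25 | 0.05 | 0.05 | 1.06 | 1.03 | 5.7% |
| 25 | 0.09 | 0.10 | 1.22 | 1.10 | 7.6% |
| 100 | 0.05 | 0.01 | 1.05 | 1.02 | 5.6% |
| 100 | 0.05 | 0.05 | 1.25 | 1.12 | 7.9% |
| 100 | 0.09 | 0.05 | 1.45 | 1.20 | 10.3% |
| 100 | 0.09 | 0.10 | 1.89 | 1.38 | 15.4% |

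As a check, contrast 3b was simulated with 12,600 against 14,700 patients. These come from 42,000 informed patients, 30% of them in the top stratum (12,600) and half of the other 29,400 given the top-10% wording (14,700); both shares are assumed. With clusters of 100 and outcome ICC 0.09, type I error was 4.6%, 6.2%, 10.6% and 14.4% at exposure ICC 0, 0.01, 0.05 and 0.10. This agrees with the formula.

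**3. Would extending the gate help?** The 15.4% row has an outcome ICC of 0.09. A rule triggered above 0.1 would leave it uncorrected.

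**4. Scale and odds ratio.** A latent-scale ICC of 0.10 corresponds to 0.078, 0.019 and 0.004 on the observed scale at outcome prevalence 50%, 5% and 1%. One threshold can therefore give different answers for vaccination and for flu diagnosis. For a small effect, the ratio of conditional to marginal log odds ratio is 1/(1 − observed-scale ICC): 1/0.922 = 1.085 at 50%, about 1.02 at 5% and 1.004 at 1%. For 51% against 50% risk, the log odds ratio is ln(0.51/0.49) = 0.0400, and an 8.5% shift moves the odds ratio from 1.041 to 1.044. The shift of 0.0034 is about 0.17 of the log odds ratio's SE (0.00488/0.25 = 0.0195).

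**The case against.** A reader might infer that the standard errors in 3b and the modality models are too small. The documents do not support that. It requires the exposure to vary between PCPs or clinics, and no exposure ICC, outcome ICC or cluster size is given. Risk stratum comes from a patient-level score, and nothing shows that it differs by clinic. Differences in portal or SMS use between clinics are plausible but not documented. With no exposure clustering the errors are correct. This stands, so the point is conditional.

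The cluster size that matters is the number of patients per PCP or clinic inside the contrast. If 100 counted all study patients, 3b would have about 100 × 27,300/56,000 = 49. Over outcome ICC 0.05 to 0.09 and exposure ICC 0.05 to 0.10, type I error would then be 6.4% to 10.1%. This also stands, and it is why the range starts at 25.

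A second tempting inference is that the primary arm comparisons are invalid when the ICC falls below 0.1. They are not: randomisation protects the error rate, and the 11% variance cost is a ceiling reached at the gate. At ICC 0.02 it is 2%. The odds-ratio shift is trivial for a small effect, and the SAP does not say that the ICC would be estimated separately for each Analysis 2 pair.

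On scope, "For both analyses described above" does not exclude the secondary outcomes, which borrow the same approach. Modality is exploratory. Contrast 3a may have been randomised, in which case the standard-error concern would not touch it. What survives is that 3b, a primary contrast, and the modality models have no protection against a plausible problem that is cheap to guard against.

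**Conclusion.** The point holds as a minor one. By its wording the rule is confined to Analyses 1 and 2 and, probably, the secondary outcomes. There it affects precision (at most about 11% of variance at ICC 0.10) and, slightly, which odds ratio is estimated. Contrast 3b and the modality comparisons are non-randomised and unprotected: their type I error is 5% if the exposure does not cluster and reaches about 15% at the top of the assumed range. The true position within that range cannot be found from the documents. Confounding in 3b and modality is a separate issue that clustered standard errors do not remove.

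**What to change.** For Analysis 3 (at least 3b) and the modality models, specify standard errors clustered on the pre-intervention PCP or clinic of record, with no ICC threshold. Name one cluster unit. Taking it from before the intervention avoids defining clusters by visits made after the messages went out.

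For Analyses 1 and 2, replace the outcome-dependent gate with one model fixed in advance and used for all arms and pairs. Either always including the PCP or clinic term, or always using logistic regression with clustered standard errors, would do. State which kind of odds ratio results.

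The cost is a few SAP sentences and, if exposure does cluster, wider intervals in 3b and modality. No new data are needed, since the protocol (Data Sources) already lists the primary care provider among the covariates to be extracted.

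### Analyses 1 and 2 omit the top-3% vs 3-10% risk stratum; adding it costs almost nothing and frees Analysis 1 from an unstated condition on the control share

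*SAP*

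**What the plan says.** The Protocol (Research Design) describes one allocation: "Patients from the high-risk sample (primary target population) will be randomly assigned to one of 4 study arms". It names no stratification factor and no allocation ratio, there or in Detailed Study Procedures.

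The SAP introduces the risk strata under Question 3: "Patients in each of the conditions were stratified based on whether they were in the top 3rd percentile of risk". Everyone else formed a lower stratum, running from 3% to 10%. The upper stratum received a single risk wording. The lower stratum received two: "Patients in the latter group were either told they were in the 'top 10%' of risk or that they were at 'high' risk".

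The stratum does not return in the two preceding primary analyses. For groups 2-4 against control, Analysis 1 says "we will employ a generalized linear model with a binary distribution and log-link function", which the SAP equates with logistic regression. Analysis 2 reads "We will evaluate this using 3 logistic regression models, comparing patients in groups 2 and 3, 2 and 4, and 3 and 4", with Holm adjustment. The only further term named for either is a PCP or clinic random effect if the ICC exceeds 0.1. The Secondary Analyses paragraph carries both approaches over to the secondary outcomes.

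Risk level enters only under Exploratory Analyses: "We will evaluate the impact of risk level (top 3rd percentile vs. remaining 3-10th percentile) as a moderator for Analysis 1", with risk framing as the moderator for Analysis 2.

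**The concern.** A factor used to stratify the patients would normally appear in the primary models. Leaving it out raises two separate questions.

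- **Precision.** If the randomisation was stratified by risk, an unstratified model does not credit the balance this produced, and its standard errors are somewhat too large.
- **Composition.** Analysis 1 pools groups 2-4 and compares them with control. If control made up a different fraction of the top-3% and 3-10% strata, the two sides would differ in risk mix, and any baseline difference between strata would be read as a message effect. The second wording in the 3-10% stratum makes this conceivable, because it creates more message cells there than in the top 3%.

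At stake is whether the answer to Question 1 holds however patients were allocated, or only under a condition that the plan leaves unsaid.

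**Working it through.** The documents give no power, alpha, baseline rate or allocation ratio, so there is no design figure to reproduce.

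**Input from the documents.** N = 56,000 (Protocol, Recruitment and Enrollment: "Anticipated enrollment number for this primary target population is 56,000").

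**Assumptions.**
- The strata divide 3:7, as the percentile bands imply: 16,800 and 39,200 patients.
- Vaccination is 50% in the 3-10% stratum and higher by a gap g in the top 3%.
- There is no true message effect, and tests are two-sided at 5%.

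**Precision, stratified allocation with control at 25% in both strata.** Control is 14,000 and informed is 42,000. The ratio of the unadjusted SE to the true SE is √[p(1−p) / Σ wₛpₛ(1−pₛ)], where p is the overall rate.
- g = 5 points: p = 0.3×0.55 + 0.7×0.50 = 0.515 and p(1−p) = 0.249775. The within-stratum variance is 0.3×0.2475 + 0.7×0.25 = 0.24925. The ratio is 1.0011 and the actual alpha 4.98%.
- g = 10 points: p = 0.53 and p(1−p) = 0.2491. The within-stratum variance is 0.3×0.24 + 0.7×0.25 = 0.247. The ratio is 1.0042 and the actual alpha 4.90%.
- g = 20 points, across lower-stratum baselines of 40-60%: the SE is too large by 1.7-1.9% and alpha is about 4.6%.

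At the 50% baseline the pairwise comparisons in Analysis 2 have the same ratios.

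**Composition, unequal control share (Analysis 1 only).** Bias = (top-3% share among informed − top-3% share among control) × g.

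Suppose all wording cells were of equal size within each stratum. The top 3% then has 4 cells (control plus three groups), and the 3-10% stratum has 7 (control plus three groups × two wordings).
- Control: 16,800/4 + 39,200/7 = 4,200 + 5,600 = 9,800, of whom 4,200/9,800 = 42.9% are top-3%.
- Informed: 12,600 + 33,600 = 46,200, of whom 12,600/46,200 = 27.3% are top-3%.
- SE at g = 5: √[0.249775 × (1/9,800 + 1/46,200)] = 0.56 points.

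| Control share, top 3% vs 3-10% | g (points) | Bias (points) | SE (points) | Type I error |
|---|---|---|---|---|
| 1/4 vs 1/4 | 5 | 0 | 0.49 | 4.98% |
| 25% vs 24% | 10 | −0.11 | 0.49 | 5.5% |
| 25% vs 20% | 5 | −0.31 | 0.51 | 9.3% |
| 25% vs 20% | 10 | −0.62 | 0.51 | 22.7% |
| 1/4 vs 1/7 | 1 | −0.16 | 0.56 | 5.9% |
| 1/4 vs 1/7 | 5 | −0.78 | 0.56 | 28.9% |
| 1/4 vs 1/7 | 10 | −1.56 | 0.55 | 80.4% |

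If higher-risk patients vaccinate more, the bias runs against the message. For flu diagnosis, at assumed rates of 2% (top 3%) and 1% (3-10%), the 1/4 vs 1/7 split gives −0.16 points against an SE of 0.13 and a type I error of 22%. Since fewer diagnoses is the hoped-for result, this would falsely favour the message.

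**With the stratum in the model.** In a simulation of the log odds ratio (40,000 runs per case; equal shares and 1/4 vs 1/7; gaps of 5, 10 and 20 points), type I error was 4.9-5.1% throughout.

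**Change of scale.** At the 50% baseline with equal shares, a stratum-conditional odds ratio of 1.20 corresponds to an unadjusted one of 1.1995 at a 5-point gap and 1.198 at 10 points.

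**The case against.** A reader might infer that the standard errors do not match the design. The documents do not support that. The SAP sentence can equally mean that patients already assigned to conditions were grouped by risk, and the Protocol describes a single four-arm assignment with no strata. Under that design the unadjusted standard errors are correct. Even under stratified randomisation the excess is under 0.5% for gaps up to 10 points, and it errs on the safe side.

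A reader might also infer that Analysis 1 is biased. That is not shown either. Four-way randomisation followed by a split of messaged 3-10% patients between two wordings leaves the control share equal in expectation; an extra wording inside the message arms does not shrink control. The 1/4 vs 1/7 case requires separate allocation by stratum over equal-sized wording cells. Control would then have 9,800 patients and each message group 46,200/3 = 15,400, an imbalance that neither document mentions. The vaccination gap is a second assumption: the score was built to predict serious flu complications, and the strata are adjacent bands.

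Finally, a moderator model for Analysis 1 would ordinarily contain the stratum main effect and give stratum-specific message effects, so a composition artefact could be noticed.

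All of this stands, and it limits the point to a conditional risk. It does not remove it. The Protocol mentions neither the strata nor the split in wording, so it cannot settle how patients were allocated within strata. The moderator models are exploratory and do not supply an adjusted primary estimate.

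**Conclusion.** The omission from Analyses 1 and 2 and their secondary-outcome versions is plain in the text. Its certain consequences are small. The loss of precision is about 0.1% to 0.4% of the standard error if randomisation was stratified with equal control shares and the gap is 5 to 10 points; there is no SE error if it was a single draw.

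What gives the point substance is that the freedom of Analysis 1 from confounding by risk level depends on equal control shares, and neither document states that condition. If it failed as far as 1/4 vs 1/7, a 5-point gap would produce a bias of about 0.8 points against an SE of 0.56; at 25% vs 24% the effect would be negligible. These figures rest on the assumed 3:7 split, 50% baseline, gaps and shares.

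The control-share argument does not reach Analysis 2. If both wordings were used in all three message groups, the extra wording gives no reason to expect a different risk mix among them. This is a free improvement, not a demonstrated defect.

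**What to change.** - State in Analyses 1 and 2, and for their use on secondary outcomes, that every model includes risk stratum (top 3% vs 3-10%) as a fixed effect.
- Report a stratum-standardised risk difference beside the odds ratio, because the odds ratio becomes conditional on stratum.
- State whether randomisation was stratified by risk, and the allocation to each group within each stratum.
- Tabulate patients by group and stratum. This settles whether the control shares were equal; if they were not, the stratum term is essential for Analysis 1.

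The cost is a few SAP sentences, one table and one model term, using a variable already needed for the moderator analyses. The shift in the odds ratio from conditioning on stratum is trivial at the gaps considered.
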